6.4 INCLUSION CRITERIA

Subjects may be enrolled in the study if they meet all the following:

- 6.4.1 Age \geq 18 years
- 6.4.2 Proximal lower extremity DVT involving the femoral, common femoral, iliac veins or inferior vena cava (IVC), alone or in combination^a
- 6.4.3 Willing and able to provide informed consent

6.5 EXCLUSION CRITERIA

Subjects will be excluded from the study for any of the following:

- 6.5.1 Prior venous stent in a TVS
- 6.5.2 IVC aplasia/hypoplasia or other congenital anatomic anomalies of the IVC or iliac veins
- 6.5.3 IVC filter in place when ClotTriever system enters the patient (Patients can be included if an existing IVC filer is removed prior to insertion of the ClotTriever system)
- 6.5.4 Allergy, hypersensitivity, or thrombocytopenia from heparin or iodinated contrast agents, except for mild to moderate contrast allergies for which pretreatment can be used
- 6.5.5 Life expectancy less than 1 year
- 6.5.6 Chronic non-ambulatory status
- 6.5.7 Known hypercoagulable states that, in the opinion of the Investigator, cannot be medically-managed throughout the study period

^a Subjects with bilateral DVT may be enrolled but will not be included in the Primary Analysis Dataset.

6.5.8 Unavailability of a proximal lower extremity venous access site^b

7 ASSESSMENTS AND FOLLOW-UP SCHEDULE

7.1 SCHEDULE OF ASSESSMENTS

The data collected will be standard-of-care. In this regard, the Schedule of Assessments comprises recommended evaluations, and any departures from the schedule will not be considered Protocol Deviations (see Section 11.3).

Table 1. Schedule of Assessments

| Assessment | Baseline* (-7 to 0 days) | Index Procedure (day 0) | Discharge | 30 Days (14 to 45 days) | 6 Months (46 to 270 days) | 1 Year (271 to 540 days) | 2 Years (541 to 900 days) | Unscheduled Visits |
|---|-----------------------------|-------------------------------|-----------|----------------------------|------------------------------|-----------------------------|------------------------------|-----------------------|
| Medical history | Х | | | | | | | |
| Physical examination† | Х | | Х | Х | Х | Х | Х | Х |
| Inclusion/exclusion criteria | Х | | | | | | | |
| Anticoagulation regimen | Х | Х | Х | Х | Х | Х | Х | Х |
| Duplex ultrasound [§] | Х | | | Х | Х | Х | Х | Х |
| Venogram (Required) | | 2x+ | | | | | | |
| IVUS (Expected) | | 2x+ | | | | | | |
| Access site examination | | | Х | Х | | | | |
| Adverse event assessment | | Х | Х | Х | Х | Х | Х | Х |
| CEAP Score | Х | | | | | | | |
| EQ-5D, Villalta, rVCSS Quality of Life Assessments | Х | | | Х | х | х | х | |
| Edema and Numeric Pain Rating Scale (NPRS) assessment | х | | x | х | Х | Х | Х | |

^{*}Baseline assessments must be performed no more than 7 days prior to the index procedure or after the onset of symptoms in those subjects with less than 7 days' symptom duration.

[†]Physical examination is limited to the involved lower extremity(ies). Examination will include an assessment of leg edema, graded as per the rVCSS scale; mild (limited to foot and ankle), moderate (above ankle but below knee), or severe (knee and above), and recorded on the right and left legs.
Duplex ultrasound will include patency assessments of all target lesions including flow (present, absent, or not evaluable) and compressibility (normal, partial, incompressible, not evaluable).

[†] Imaging will be captured before ClotTriever treatment and after ClotTriever treatment but before adjunctive therapy (if any). If adjunctive therapy is utilized, a third set of images will be obtained afterwards. In addition, if a reintervention is performed, the same imaging timing and transfer are required. Note that adjunctive therapy is defined as an additional thrombus removal strategy after ClotTriever thrombectomy has been completed (i.e. balloon, stenting, and placement of IVC filters during ClotTriever procedure session would NOT be considered adjunctive therapy).

CEAP (Clinical, Etiologic, Anatomic, and Pathophysiologic) score is a clinical classification score developed to allow uniform diagnosis and stratification of patient populations according to the severity of their presentation

^b For example, from a popliteal, femoral or other infrainguinal vein on either side. Jugular access is not allowed.

7.2 BASELINE ASSESSMENT

The Baseline Assessment includes diagnostic testing, patient status, and eligibility verification for study participation including:

- Review inclusion/exclusion to ensure patient meets criteria
- Review duration of symptoms
- Confirm venous thrombus presence on duplex ultrasound

If the patient meets all eligibility criteria and is scheduled for the thrombectomy procedure, the patient may be invited to participate in the study.

The data captured for the Baseline Visit may be gathered over the course of more than one office visit; however, the data must have been obtained within 7 days of the scheduled index procedure date and, for subjects with symptoms of less than 7 days' duration, after the onset of symptoms.

The following procedures will be performed at Baseline prior to the index procedure. All data must be recorded in the subject's case report forms (CRF):

- Demographic information
- Medical history including risk factors
- Physical examination including an edema evaluation of both legs^c
- Presence of relative and absolute contradictions to pharmacologic thrombolysis
- Anticoagulation Regimen
- Duplex ultrasound assessment of patency of the TVS
- CEAP Score
- EQ-5D, Villalta, rVCSS,
- Edema and Numeric Pain Rating Scale (NPRS)

Clinical laboratory tests are expected to be performed at this visit to establish baseline levels (i.e., creatinine, platelet counts, and INR if subject is on warfarin). The panel of tests standardly performed at the institution for patients with similar conditions related to DVT should be considered. It is recognized that specific panels may vary between institutions. Laboratory data will not be specially analyzed but will be used to support adverse event (AE) evaluations.

Subjects with bilateral DVT may be enrolled. Each leg's TVS will be counted separately in the 500-subject Full Analysis dataset. The second leg may only be enrolled and treated at the time of the primary leg's index procedure.

^c Measurements are to be taken from three locations: (1) Thigh = midpoint between the hip and the proximal edge of the patella; (2) Mid-Calf = midpoint between the tibial tuberosity and the medial malleolus; and (3) Ankle = 2 cm about the medial malleolus.

7.3 INDEX PROCEDURE

Thrombectomy using the ClotTriever System is considered the index procedure and the treatment phase of the study. The procedure is conducted under fluoroscopic/angiographic guidance. Refer to the Instructions for Use (IFU) for techniques and methods for device deployment.

Anticoagulation therapy to ensure an activated clotting time of 250 – 300 seconds is recommended.

Subjects who require conversion to open surgery due to treatment failure with the device will be followed for safety through 30 days, or until any treatment related adverse events resolve, which ever is later.

The following data are to be recorded on the subject's Procedure CRF.

- Length of procedure (from ClotTriever sheath access to last removal of sheath)
- Number of ClotTriever passes
- Number of ClotTriever devices used, with lot numbers
- Largest sheath size used
- Pre- and post-procedure venogram findings
- Pre- and post-procedure IVUS measurements
- Concurrent use of balloon angioplasty and/or stenting and/or placement of IVC Filter
- Adjunctive therapy (thrombolysis and/or additional thrombectomy).
- Anticoagulant used and amount

Venogram runs/cines must be, and IVUS runs should be, acquired pre-ClotTriever and post-ClotTriever^d. If adjunctive therapy is used, a third venogram and IVUS run post-therapy will be acquired. All procedural venograms cines and IVUS images will be de-identified, labeled appropriately, uploaded and sent to the Core Laboratory.

7.4 TARGET VESSEL SEGMENT (TVS) ASSIGNMENT

The target vessel segment (TVS) is thrombus-containing venous segments, specified by the operator, that were treated with the study device at the index procedure. These segments may include the popliteal vein, caudal femoral vein, cranial femoral vein, profunda/deep femoral vein, common

femoral vein, external iliac vein, internal iliac vein, common iliac vein, or the inferior vena cava. The TVS does not include segments that were not intentionally treated but were instead passed through to remove the device from the leg.

All vessels treated in one leg/side are recorded under one TVS. There are three possible TVS designations:

- For unilateral treatment: TVS 1 = Leg 1 and can be any or all segments from the IVC to the popliteal
- For bilateral treatment only: TVS 2 = Leg 2 and will not include the IVC (if the IVC was treated, record it as part of TVS 1)
- For IVC treatment only: Neither leg was treated, and the treatment was IVC only (designate as TVS 1)

d Ballooning and/or stenting and/or IVC placement during the procedure is routine and not considered adjunctive therapy. Adjunctive therapy includes thrombolysis and additional thrombectomy

7.5 CLINIC/HOSPITAL DISCHARGE ASSESSMENT

Subjects will be evaluated during the time after procedure completion and prior to clinic/hospital release. The following information will be collected on the Discharge CRF:

- Time spent in ICU and hospital
- Physical examination of the target proximal lower extremity(ies), including an edema evaluation of both legs
- Anticoagulation regimen
- Examination of access site for wound complications
- Rethrombosis since leaving the procedure room
- Reintervention since leaving the procedure room
- AE observations
- Blood transfusions
- Edema and Numeric Pain Rating Scale (NPRS)

Thrombus removal interventions that are performed at the end of the index procedure prior to the subject leaving the procedure room will be reported as adjunctive procedures and are not tabulated as reinterventions. In addition, before the subject has left the procedure room, formation of thrombus within the treated TVS is not reported as a rethrombosis when it occurs during the index procedure.

7.6 FOLLOW-UP ASSESSMENTS AND WINDOWS

Follow-up evaluation will be scheduled at 30 days (14-45 days), 6 months (46-270 days), 1 year (271-540 days), and 2 years (541-900 days) post-procedure. The following assessments and procedures will be performed at each follow-up visit:

- Physical examination of the target proximal lower extremity(ies), including an edema evaluation of both legs
- Anticoagulation regimen
- Duplex ultrasound of TVS for patency^e
- Rethrombosis since the last visit
- Reinterventions since the last visit
- AE observations that occurred since the last visit
- Quality of life indices (EQ-5D, Villalta, and rVCSS)
- Edema and Numeric Pain Rating Scale (NPRS)

7.7 PROCEDURES, REINTERVENTIONS, AND RETHROMBOSIS

After the index procedure, conditions warranting additional treatment may present. Any intervention taken to treat a condition involving the initially treated TVS shall be documented. Adjunctive therapy is defined as an

^e Duplex ultrasound will also be performed at unscheduled visits when the reason for the visit was potentially a patency-related event. The duplex ultrasound examination will specify whether each TVS was a) normal (compressible with flow), b) abnormal but patent (partially compressible with flow), or c) occluded (absent flow or incompressible). In the presence of a double femoral vein and when only one of the veins was treated, the sonographer must be certain to perform the duplex ultrasound assessment on the treated vein.

additional thrombus removal strategy after ClotTriever thrombectomy has been completed (i.e. balloon, stenting, and placement of IVC filters during ClotTriever procedure session would NOT be considered adjunctive therapy).

If a subject requires TVS venography during the follow-up period, the images must be sent to the core laboratory for analysis. For any TVS reintervention, pre- and post-reintervention images must also be sent.

7.8 UNSCHEDULED FOLLOW-UP VISITS

This Registry study was designed to capture real-world data regarding the clinical use of the ClotTriever Thrombectomy System. Therefore, the study will only record subject visits during the follow-up period that are related to the subject's DVT condition and treatment. If a subject returns to the site between scheduled follow-up visits for matters related to the study, the visit will be treated as an unscheduled visit and the assessments completed at this visit will be done at the discretion of the Investigator. CRF pages are provided for unscheduled visits and contain the same information as all the follow-up visits, in addition to the reason for the visit.

7.9 WITHDRAWALS AND LOST TO FOLLOW-UP

Participation is completely voluntary, and each subject is free to withdraw from the study at any time. An investigator also has the right to withdraw the subject from the study in the event of reasons concerning the health or well-being of the subject, or in the case of lack of cooperation. Should a subject decide to withdraw for any reason, or should the investigator decide to withdraw the subject, all efforts will be made to complete and report the observations up to the time of withdrawal as thoroughly as possible. A complete final evaluation at the time of the subject's withdrawal must be made and an explanation given as to why the subject is withdrawing or being withdrawn from the study.

The reason for and date of withdrawal must be recorded on the subject's End of Study/Study Exit CRF. If the reason for the withdrawal is a device-related or procedure related AE, the event must be reported to the Sponsor and recorded in the CRF.

If the procedure is aborted, the subject does not need to complete the follow-up assessments, unless the subject is converted to surgical repair. Subjects who require conversion to open surgery due to treatment failure with the device will be followed for safety through 30 days, or until any treatment related adverse events resolve, which ever is later. The subject's enrollment roster position may not be made available to other subjects (i.e., the subject will not be replaced).

All efforts will be made to return subjects for all the follow-up visits. Due diligence in reaching the subject must be made by two documented telephone contact attempts, emails, or regular postal mail letters. After the above attempts are made, if no response is obtained, the final evaluation of the subject will be the last visit at which study-related procedures were performed. The End of Study/Study Exit CRF page will be completed, and communication attempts will be documented.

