4 STUDY OBJECTIVES

The primary objective of this study is to evaluate real world patient outcomes after treatment of acute, subacute, and chronic proximal lower extremity DVT with the ClotTriever Thrombectomy System.

Secondary objectives will consist of the following:

- Assessment of post-thrombotic syndrome, as defined by the Villalta scale³¹
- Assessment of symptomatic improvement using the change in venous quality of life indices
- Determination of patency (primary, assisted primary, and secondary)
- Differences in outcome in the acute (≤14 days), subacute (>14 days ≤6 weeks), and chronic (>6 weeks) cohorts and in other subsets (see Section 10)

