6 STUDY DESIGN

The CLOUT Registry is a prospective, multi-center, observational study of subjects with proximal lower extremity DVT treated with the ClotTriever Thrombectomy System. The Registry will collect data on demographics, comorbidities, details from the DVT diagnosis and treatment, and clinical outcomes through 2-year follow-up.

Up to 500 subjects with proximal lower extremity DVT will be enrolled at up to 50 Registry sites. All subjects who sign consent and are treated with the ClotTriever System will comprise the Full Analysis dataset.

The Primary Analysis datasets will be derived from the 500 subject Full Analysis dataset. Hypothesis testing will be performed on this dataset; the safety endpoint testing will be performed on the Primary Analysis Safety cohort and the effectiveness endpoint testing will be performed on the Primary Analysis Effectiveness Cohort.

- The Primary Analysis Safety cohort will include the first 91 subjects that enroll with a clinical presentation analogous to that used for the literature-derived performance goal (i.e., unilateral acute or subacute DVT of less or equal to 6 weeks' duration). These first 91 subjects will not have been not treated with thrombolytic or percutaneous mechanical thrombectomy within the prior 3 months.
- From these same 91 subjects, the Primary Analysis Effectiveness cohort will be the subset of subjects who undergo treatment with the ClotTriever System in venous segments with Core Laboratory determined intraluminal thrombus.

Once the Primary Analysis cohort is fully accrued, subjects meeting these criteria will continue to be enrolled and will be evaluated as part of the Full Analysis dataset.

The primary safety endpoint will be assessed when the 30-day follow-up data on the 91-subject Primary Analysis cohort is complete (see Section 10.4), allowing evaluation of both the primary safety and effectiveness endpoints. The remainder of the subjects will be enrolled to obtain additional safety and effectiveness data and to allow subset analyses of various pre-determined subgroups. Subjects in both arms will be followed for 2 years after the index procedure.

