6.3 Point of Enrollment

The ClotTriever System is not being used in an investigational manner and the patient will be treated with the device in the same manner regardless of whether the patient enrolls in the study. Therefore, the patient's consent for treatment is covered under the institution's internal procedures. To participate in the study, the patient must consent to share his/her deidentified personal health information (PHI) with the study sponsor. This allows sites to treat patients prospectively and consent patients after treatment. This can be helpful for sites when the research staff is unavailable to consent the patient prior to the index procedure (i.e., after hours, weekends, holidays). This practice is allowed provided there is no institutional prohibition against post-procedure consent.

Pre-procedure consents are the preferred consenting method and should be obtained within 7 days of the scheduled index procedure as part of the baseline work-up. When post-procedure consents are obtained, the consent must be obtained after the patient gains full capacity after anesthesia and within 7 days of the index procedure.

If the ClotTriever System does not enter the patient's vasculature, the patient is considered a screen failure and as such, his/her data is not to be entered into the database. A patient is considered enrolled when 1) the device enters the patient and 2) the patient consents to the study. The timing of the two events, index procedure and consent, are interchangeable.

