3.2. Primary Analysis Population

The Primary Analysis dataset is a subset of subjects with unilateral acute or subacute DVT of less than or equal to a 6-week duration, without recent (≤ 3 months) venous intervention. The first 91 subjects enrolled who meet these criteria will complete the Primary Analysis dataset. Enrollment of this type of subject will continue once the Primary Analysis cohort is fully accrued, i.e., past the 91 subjects needed for the primary endpoint analyses. These additional subjects will be included in the Full Analysis dataset.

4. Incomplete Date Handling and Missing Data

Incomplete dates will follow the following imputation assignment rules:

1. If day is missing but month and year are present, the day will be set to the first date of the month.
2. If both day and month are missing but year is present, then January 1st will be used as the imputed value.
3. If year is missing, then the date is considered missing. In general, missing data points are not imputed.

Subjects with missing effectiveness data will be assumed to have data missing at random and will be imputed by random selection with replacement of data from subjects with pre- and post-intervention measurement of thrombus removal. By repeating this process, e.g. for 5,000 separate data replicates, an empirical distribution of primary effectiveness endpoint can be derived for an estimated 95% confidence interval based on the quantiles of the empirical distribution. The robustness of the multiple imputation outcome will be tested with a tipping point analysis encompassing all possible imputation outcomes.

5. Statistical Methods and Analysis

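### Aborted and surgically converted procedures drop out of the 2-year outcome data, and aborted ones out of the required 30-day visit, although both are enrolled and not replaced

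*Protocol*

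**What the plan says.** Protocol section 6 states: "Subjects in both arms will be followed for 2 years after the index procedure". SAP section 2 repeats the sentence, and neither names an exception.

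Protocol 7.9 then sets a different rule for two kinds of subject:

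- **Aborted procedure.** "If the procedure is aborted, the subject does not need to complete the follow-up assessments, unless the subject is converted to surgical repair".
- **Conversion to open surgery.** "Subjects who require conversion to open surgery due to treatment failure with the device will be followed for safety through 30 days" (7.3, repeated in 7.9), with the extension "or until any treatment related adverse events resolve, which ever is later".

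These subjects are in the study. Protocol 6.3 puts enrolment at device entry plus consent: "A patient is considered enrolled when 1) the device enters the patient and 2) the patient consents to the study". Protocol 7.9 adds that "the subject will not be replaced".

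The outcomes affected include a stated secondary objective, "Assessment of post-thrombotic syndrome, as defined by the Villalta scale" (Protocol section 4), and the rVCSS, pain and EQ-5D comparisons with baseline in Protocol 5.3 and SAP 2.3. The SAP has no rule for aborted or converted subjects in any analysis. Its section 4 says "In general, missing data points are not imputed", in the list on incomplete dates, and then sets out imputation for missing effectiveness data only.

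**The concern.** Whether a subject's later data are collected depends on how the procedure went. That makes the loss systematic: it comes from a written rule and is likely to be related to outcome. A registry whose stated aim is real-world outcome would report Villalta, symptom and quality-of-life results that leave out two of the less favourable procedural courses, and nothing in the SAP would make the omission visible.

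The waiver also touches the primary safety endpoint. The 30-day visit is one of the follow-up visits in Protocol 7.6, so an eligible aborted subject can hold one of the first 91 places with no scheduled visit at which MAE status is established. Converted subjects are better covered at that time point, because their safety follow-up runs for at least 30 days.

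**Working it through.** **1. The passages side by side.**

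| Subject | Required follow-up | Source |
|---|---|---|
| Any subject | 2 years | Protocol 6, SAP 2 |
| Aborted, not converted | Follow-up assessments not required | Protocol 7.9 |
| Converted to open surgery | Safety only; 30 days or until treatment-related events resolve, whichever is later | Protocol 7.3, 7.9 |
| Completed, under 75% removal, or adjunctive therapy, rethrombosis or reintervention | Visits to 2 years | Protocol 7.6; no exception stated |

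Read alone, the exception for surgical repair in 7.9 might seem to keep converted subjects on the full schedule. The sentence after it describes safety follow-up only.

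**2. The plan's own safety figure, reproduced.** Inputs from Protocol 10.8 and SAP 5.1: performance goal 34%, anticipated MAE rate 20%, one-sided exact binomial test at 0.025. The rule is the largest c with P(X ≤ c | n, 0.34) ≤ 0.025, and power is P(X ≤ c | n, 0.20).

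- n = 86: c = 20, exact alpha 0.0209, power 81.5% (stated 82%).
- 86 / 0.95 = 90.5, rounded up to 91 (stated 91).

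The plan's numbers hold.

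**3. What missing 30-day status does near the boundary.** By the same rule:

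| Subjects analysed | Most MAEs that still pass | Exact alpha |
|---|---|---|
| 91 | 21 | 0.0162 |
| 88 (3 without status, excluded) | 20 | 0.0149 |
| 86 (5 without status, excluded) | 20 | 0.0209 |

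Three and five subjects are illustrations. With three aborted subjects of unknown status:

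- 21 MAEs among the other 88 fail if the three are excluded (21 > 20), but pass if they are counted as event-free (21 of 91).
- 20 MAEs among the 88 pass if the three are excluded, but fail if they are counted as events (20 + 3 = 23 > 21).

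If unknown status counts as an event, the observed subjects may have at most 21 − 3 = 18 MAEs, or 21 − 5 = 16 with five unknown. Neither document says which convention applies.

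**4. Size of the effect on the PTS rate.** Let f be the share aborted or converted, p the PTS rate in those followed and q the rate in those not followed. The rate in all enrolled is (1 − f)p + fq, so the reported rate is too low by f(q − p). The documents give none of the three. Assumed: f = 1% to 10% (about 1 to 9 of 91), p = 30%, q = 50%.

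- f = 1%: 0.01 × 20 = 0.2 points (30.0% reported, 30.2% in all).
- f = 10%: 0.10 × 20 = 2.0 points (30.0% reported, 32.0% in all).

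**5. How many technical failures stay in follow-up.** Protocol 10.8 anticipates 50% Technical Success. Suppose every aborted or converted subject is a technical failure. The share of failures among those followed is then (0.50 − f)/(1 − f):

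- f = 1%: 0.49/0.99 = 49.5%.
- f = 10%: 0.40/0.90 = 44.4%.

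**The case against.** The strongest reply is that 7.9 is a specific exception to a general statement, that it is permissive, and that little is lost by it. Much of this stands.

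- **Safety reporting continues.** Protocol 9.2 keeps bleeding, access-site complications, 30-day symptomatic PE, rethrombosis, all device- or procedure-related events and any death reportable, with no exemption for aborted cases. The discharge assessment in 7.5 is separate from the follow-up visits. A reader might infer that harm after an abort goes unrecorded; the documents do not support that. What is lost is the scheduled contact at which a site would learn of an event.
- **Switching to another therapy does not end follow-up.** Thrombolysis or further thrombectomy after use of the device is adjunctive therapy (7.3, footnote), and nothing stops follow-up for it. A gap opens only if the case is recorded as aborted.
- **Thirty days is a minimum** for conversions, and follow-up after an abort is optional, not forbidden.
- **Some endpoints do not apply.** The TVS is by definition a treated segment (7.4), and rethrombosis requires documented patency beforehand (section 15). A subject aborted before any segment was treated has neither outcome, and adding such subjects to those denominators would dilute the rethrombosis rate in the device's favour.
- **Removing the waiver does not guarantee data.** Table 1 lists recommended evaluations, and departures are not deviations (7.1). Even so, gaps would no longer follow from a rule tied to procedural outcome.
- **The endpoints in question are secondary** and carry no hypothesis test.

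Reading 7.9 as an intended exception does not settle the matter. Section 6 and SAP section 2 do not mention it, and the SAP does not say how the exempted subjects are analysed.

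**Conclusion.** The point holds in a limited form. The follow-up statements conflict, and the rule in 7.3 and 7.9 removes long-term PTS, symptom and quality-of-life data for aborted and surgically converted procedures. For aborted subjects it also removes the required 30-day visit behind the primary safety endpoint.

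Two stronger readings are tempting and should not be drawn. The first is that the long-term results come only from patients in whom the device worked. Completed procedures with under 75% removal stay in follow-up, and under the plan's own 50% assumption they would be 44% to 50% of those followed. An abort is also not necessarily a device failure, since its reasons are not defined. The second is that the bias could be large because Protocol 1.4 cites about 50% PTS within 2 years on anticoagulation. That is an absolute rate. If subjects not followed had 50% PTS, a 50-point excess would require 0% in everyone else.

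The size cannot be taken from the documents. Under the assumed 1% to 10% affected and a 20-point excess, reported PTS is about 0.2 to 2 points too low. For safety, a few unknown statuses matter only near the boundary of 20 or 21 events. No planned sample size changes. This is a modest defect that is cheap to remove.

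**What to change.** Reconcile Protocol 7.3 and 7.9 with Protocol section 6 and SAP section 2 by removing the data-collection waiver. This concerns what is recorded, not how anyone is treated.

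- For every enrolled subject, including aborted and converted cases, collect 30-day MAE status, and collect Villalta, rVCSS, NPRS and EQ-5D on the Table 1 schedule to 2 years.
- Flag aborted or converted status in the database and the tables.
- In the SAP, include these subjects in the denominators for 30-day MAE, PTS, symptoms and quality of life.
- Limit TVS patency and rethrombosis to subjects with a treated TVS; rethrombosis also needs documented restored patency.

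The cost is a protocol and SAP amendment, a few extra standard-of-care visits to record, and possibly slightly less favourable long-term results. The 91-subject target is unaffected.
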